5.1.5 Criteria for Continuation of Treatment

Subjects in the ASP015K 100 mg, ASP015K 150 mg, or placebo groups who completed the assessment at study visit at Week 52 may participate in an extension study (015K-CL-RAJ2) if they wish to do so. Subjects in the reference group will not be eligible for participation in the open-label extension study. Each subject must provide informed consent for the extension study before completing the assessment at study visit at Week 52.

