WHO-DD	World Health Organization Drug Dictionary
WPAI	Work Productivity and Activity Impairment Questionnaire

List of Key Terms

Terms	Definition of terms
Baseline	1) Values/findings observed prior to the initiation of study treatment, which are regarded as the starting point for comparison. 2) The time point at which those reference values/findings were observed.
Study period	The period of time from obtaining informed consent from the subject to the end of the final evaluation/observation specified in the protocol.
Investigational period	The period of time where major interests of protocol objectives are observed. In general, the subject will receive a test drug, comparative drug, or reference drug (possibly without randomization) during this period, which extends until the last post-treatment assessment is completed.
Follow-up period	The follow-up period will be 4 weeks (on a per-protocol basis) starting after the early-termination visit for withdrawn subjects and after the Week 52 visit for subjects who completed the study but are not willing to enroll into the extension study or those in the reference group who completed the study. For subjects who completed the study and wish to enroll into the extension study, the follow-up period will last for a maximum of 4 weeks starting after the Week 52 visit and ending at the initiation of the extension study treatment.
Subject	An individual who participates in a clinical study as a recipient of either the test drug(s) or reference drug(s), or as a control.
Week 12/ET	Week 12 or early termination before Week 12
EOT	Week 52 or early termination before Week 52
Study discontinuation	The act of concluding participation, prior to completion of all protocol-required elements, in a study by an enrolled subject. Four categories of discontinuation are distinguished: a) dropout: Active discontinuation by a subject (also a noun referring to such a discontinued subject); b) discontinuation initiated by the investigator or other responsible personnel (e.g., for cause); c) loss to follow-up: discontinuation of participation without notice or action by the subject; d) sponsor-initiated discontinuation. Note that subject discontinuation does not necessarily imply exclusion of subject data from analysis.
Variable	A characteristic under study that varies: any attribute, phenomenon, or event that can have different qualitative or quantitative values.

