7.11.6 Handling of Schedule of Assessments of Safety Variables

For data obtained after the end of study treatment, the data obtained within + 2 days after the last dose is taken will be included in analysis. For data after the end of reference treatment, data obtained within + 9 days after the last dose will be included in analysis. Baseline for safety is defined as last non-missing value before the first dose of study drug or reference drug for all subjects including placebo assigned subjects. For Week 12/ET, the values at closest date to reference date will be used. As for the subjects who switched to receive ASP015K instead of placebo, the last observation before first dose of ASP015K at Week 12 will be used for the analysis for visit Week 4, 8, 12, 12/ET. For EOT, the closest value to the reference date will be used regardless of the switching from placebo.

- (1) Physical examination, vital signs, laboratory test [hematology, biochemistry, urinalysis, and pregnancy test (serum and urine)]

Table 12. Visit Window for Physical examination, vital signs, laboratory test (hematology, biochemistry, urinalysis, and pregnancy test (serum and urine))

Time points defined in analysis	Reference date*	Acceptable time range
Screening	Day -28 to Day -1	Day -28 to Day -1
Baseline	Day 1	Day 1
Week 4 to Week 48**	Day $7 \times x + 1$	Day $(7 \times x - 6)$ to Day $(7 \times x + 8)$ and before the initiation of treatment with the study drug or reference drug on the visit day
Week 52	Day 365	Day 358 to Day 372
Minimum on Treatment up to Week 12***		Minimum value at allowance Range (Day 2 to Day 92) before first dose of Week 12 study drug
Maximum on Treatment up to Week 12***		Maximum value at allowance Range (Day 2 to Day 92) before first dose of Week 12 study drug
Minimum on Treatment***		Minimum value during Entire Period (No limitation for period)
Maximum on Treatment***		Maximum value during Entire Period (No limitation for period)
Week 12/ET (Week 12 or at early termination before Week 12)	Day 85	Day 2 to Day 92
EOT (Week 52 or at early termination)	Day 365	Day 2 to Day 372

*: Day 1 represents the first day of study or reference treatment. The day before the initiation of treatment with the study drug or reference drug is expressed as Day -1.

** : Represents the reference date and acceptable time range for Week x.

***: Applied to laboratory test only.

(2) Laboratory test (fasting lipid profile test)

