Table 13. Visit Window for Laboratory test (fasting lipid profile test)

Time points defined in analysis	Reference date*	Acceptable time range
Baseline	Day 1	Before the initiation of treatment with the study drug or reference drug on Day 1 and at least 8 hours after the last meal If Baseline data is not measured at Day 1, then the closest day up to Day 1 after Day -28 will be used for Baseline.
Week 12	Day 85	Day 78 to Day 92
Week 20	Day 141	Day 134 to Day 148
Week 28	Day 197	Day 190 to Day 204
Week 40	Day 281	Day 274 to Day 288
Week 52	Day 365	Day 358 to Day 372
Minimum on Treatment up to Week 12		Minimum value at allowance Range (Day 2 to Day 92) before first dose of Week 12 study drug
Maximum on Treatment up to Week 12		Maximum value at allowance Range (Day 2 to Day 92) before first dose of Week 12 study drug
Minimum on Treatment		Minimum value during Entire Period (No limitation for period)
Maximum on Treatment		Maximum value during Entire Period (No limitation for period)
Week 12/ET (Week 12 or at early termination before Week 12)	Day 85	Day 2 to Day 92
EOT (Week 52 or at early termination)	Day 365	Day 2 to Day 372

*: Day 1 represents the first day of study or reference treatment. The day before the initiation of treatment with the study drug or reference drug is expressed as Day -1.

(3) 12-lead ECG, Chest radiography

Table 14. Visit Window for 12-lead ECG

Time points defined in analysis	Reference date*	Acceptable time range
Screening	Day -28 to Day -1	Day -28 to Day -1
Week 28	Day 197	Day 190 to Day 204
Week 52	Day 365	Day 358 to Day 372
EOT (Week 52 or at early termination)	Day 365	Day 2 to Day 372

*: Day 1 represents the first day of study or reference treatment. The day before the initiation of treatment with the study drug or reference drug is expressed as Day -1.

(4) Body weight

Table 15. Visit Window for Body weight

Time points defined in analysis	Reference date*	Acceptable time range
Screening	Day -28 to Day -1	Day -28 to Day -1
Week 12	Day 85	Day 78 to Day 92
Week 28	Day 197	Day 190 to Day 204
Week 40	Day 281	Day 274 to Day 288
Week 52	Day 365	Day 358 to Day 372
Week 12/ET (Week 12 or at early termination before Week 12)	Day 85	Day 2 to Day 92
EOT (Week 52 or at early termination)	Day 365	Day 2 to Day 372

*: Day 1 represents the first day of study or reference treatment. The day before the initiation of treatment with the study drug or reference drug is expressed as Day -1.

(5) QT assessment (except the reference group)

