Table 23 summarizes the analyses of Clinical Laboratory Evaluation, Vital Signs, and Electrocardiograms (ECGs), with "X1", "X2", "X3" indicating that the variable will be analyzed by each defined groups defined footnote. All analyses will be based on the SAF.

Table 23. The overview of Clinical Laboratory Evaluation, Vital Signs, and Electrocardiograms (ECGs) analyses

	Screening, Baseline, Weeks 4, 8, 12, 12/ET	Screening, Baseline, Weeks 4, 8, 12, 16, 20, 24, 28, 32, 36, 40, 44, 48, 52, EOT
Clinical Laboratory Evaluation		
Quantitative Laboratory Test Results in SI Units, Hematology Actual and Change from Baseline	X1 ^{#1}	X2 ^{#1}
Quantitative Laboratory Test Results in SI Units, Biochemistry Actual and Change from Baseline	X1 ^{#1}	X2 ^{#1}
Quantitative Laboratory Test Results in SI Units, Urinalysis Actual and Change from Baseline	X1 ^{#1}	X2 ^{#1}
Qualitative Laboratory Test Results, Urinalysis	X1 ^{#2}	X2 ^{#2}
Quantitative Laboratory Test Results in SI Units, Fasting Lipids Profile Actual and Change from Baseline	X1 ^{#1}	X2 ^{#1}
Quantitative Laboratory Test Results in SI Units, T-Chol/HDL, LDL/HDL Ratio Actual and Change from Baseline	X1 ^{#1}	X2 ^{#1}
Quantitative Laboratory Test Results in SI Units, Erythrocyte Sedimentation Rate (ESR) Actual and Change from Baseline	X1 ^{#1}	X2 ^{#1}
Shift-from-Baseline Table for Laboratory Test Results, Hematology Baseline to Lowest Value up to Week 12 /EOT	X1	X3
Shift-from-Baseline Table for Laboratory Test Results, Hematology Baseline to Highest Value up to Week 12 /EOT	X1	X3
Shift-from-Baseline Table for Laboratory Test Results, Biochemistry Baseline to Lowest Value up to Week 12 /EOT	X1	X3

Shift-from-Baseline Table for Laboratory Test Results, Biochemistry Baseline to Highest Value up to Week 12 /EOT	X1	X3
Shift-from-Baseline Table for Laboratory Test Results, Urinalysis Baseline to Lowest Value up to Week 12 /EOT	X1	X3
Shift-from-Baseline Table for Laboratory Test Results, Urinalysis Baseline to Highest Value up to Week 12 /EOT	X1	X3
Shift-from-Baseline Table for Laboratory Test Results, Fasting Lipid Profile Baseline to Lowest Value up to Week 12 /EOT	X1	X3
Shift-from-Baseline Table for Laboratory Test Results, Fasting Lipid Profile Baseline to Highest Value up to Week 12 /EOT	X1	X3
Shift-from-Baseline Table in Pre-Specified Reference Range Laboratory test Results by Visit, Selected Laboratory Variables	X1 ^{#1}	X2 ^{#1}
Aspartate Aminotransferase (AST)	X1 ^{#1}	X2 ^{#1}

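### SAP Tables 12 and 13 set no date limits on the overall on-treatment laboratory extremes, contradicting the SAP's own cut-offs and letting pre-dose and off-drug values in

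*SAP*

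**What the plan says.** SAP 7.11.6, Table 12 (haematology, biochemistry, urinalysis) has two rows for the overall on-treatment extremes: "Minimum value during Entire Period (No limitation for period" and "Maximum value during Entire Period (No limitation for period". Table 13 repeats both for fasting lipids. The corresponding rows for the first 12 weeks are bounded: "Maximum value at allowance Range (Day 2 to Day 92) before first dose of Week 12 study drug".

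The opening paragraph of the same section sets a general limit for safety data after study treatment ends: "the data obtained within + 2 days after the last dose is taken will be included in analysis". For etanercept the limit is +9 days.

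SAP 7.5.2 uses the entire-period extremes for three outputs: shifts from baseline to the highest or lowest value, shifts in toxicity grade to the worst value, and the Table 7 counts of subjects by highest or lowest value. Appendix 4, Table 23 describes the high-value shifts as "Baseline to Highest Value up to Week 12 /EOT". The EOT window in Tables 12 and 13 is Day 2 to Day 372.

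SAP 7.5.2.1 brings in two further periods. Liver maxima use the investigational period, which runs to the last post-treatment assessment. Liver plots use the study period, defined as "The period of time from obtaining informed consent from the subject to the end of the final evaluation/observation specified in the protocol". No sentence says which window prevails.

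**The concern.** A row labelled on treatment should hold values taken on treatment. The parenthesis in Tables 12 and 13 waives date limits, so a programmer who follows it applies no filter. Screening draws, the Day 1 pre-dose draw and the follow-up draw then qualify. An abnormality that predates the first dose, or arises weeks after the last, would be reported as occurring on drug in the overall-period shift tables and Table 7 counts.

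The follow-up draw is also not equally available. Protocol 5.1.5 states: "Subjects in the reference group will not be eligible for participation in the open-label extension study". Etanercept completers are therefore all due follow-up. The second footnote to the Schedule of Assessments removes it for subjects who start the extension immediately after Week 52. Table 23 presents the overall shift tables for 100 mg, 150 mg and the reference group, so the imbalance falls between displayed columns.

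**Working it through.** **1. The windows side by side**

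| Place in SAP | Start | End |
|---|---|---|
| Tables 12 and 13, overall rows | none | none |
| Tables 12 and 13, Week 12 rows | Day 2 | Day 92, before the Week 12 dose |
| 7.11.6, opening rule | not stated | last dose +2 days (study drug) or +9 days (etanercept) |
| Table 23, using the EOT window | Day 2 | Day 372 |
| 7.5.2.1, liver maxima | start of investigational period | last post-treatment assessment |
| 7.5.2.1, liver plots | consent | final observation |

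**2. Which pre-dose values could enter.** Exclusion criterion 13 caps screening values. Comparing it with SAP Table 7:

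- Lymphocytes: excluded below 800/µL, so 800 to 1,499 falls in the band from 500 to below 1,500.
- Neutrophils: excluded below 1,000/µL, so 1,000 to 1,499 falls in the band from 500 to below 1,500.
- ALT: excluded at 2×ULN or above, so 1 to below 2×ULN falls in the lowest listed band.
- Haemoglobin: excluded below 9.0 g/dL, so 9.0 to below 10.0 falls in the band from 8.0 to below 10.0.
- CPK: no screening limit, so any band is reachable.

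Fasting lipids are not scheduled at screening. Table 13 is exposed through Day 1 and follow-up.

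**3. A false shift.** Take a subject with screening ALT 1.8×ULN (eligible), and normal ALT on Day 1 and at every visit on drug. Safety baseline is the last non-missing value before the first dose, so it is normal. The literal maximum is 1.8×ULN, and the subject is tabulated as moving from normal to high. With a Day 2 start the subject stays normal.

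A Day 1 value that is itself the baseline cannot do this. Including it does mean the maximum can never lie below baseline, so a subject high on Day 1 and normal throughout treatment still counts as high.

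**4. Timing of follow-up.** Assume a Week 52 visit on Day 365, a last oral dose the day before (Day 364), and a last etanercept dose at Week 51 (7 × 51 + 1 = Day 358). Follow-up is 28 ± 7 days after Week 52: 365 + 21 = Day 386 to 365 + 35 = Day 400.

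- Study drug: 386 − 364 = 22 to 400 − 364 = 36 days after the last dose, against a limit of 2.
- Etanercept: 386 − 358 = 28 to 400 − 358 = 42 days, against a limit of 9.

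Both also lie beyond Day 372. The opening rule or the EOT window would exclude this draw; the unbounded row admits it.

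**5. Inequality of follow-up.** Let f be the share of subjects in the two ASP015K arms who have a follow-up draw (assumed; not in the documents). Use planned sizes of 100 + 100 and 200, with every etanercept subject having the draw. The etanercept share of follow-up draws is 200/(200 + 200f):

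- f = 5%: 200/210 = 95%
- f = 20%: 200/240 = 83%
- f = 50%: 200/300 = 67%
- f = 100%: 200/400 = 50%, equal to its share of subjects.

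**6. Effect of extra draws.** A completer has 13 scheduled post-baseline chemistry and haematology draws (Weeks 4 to 52), 14 with follow-up, and 16 with screening and Day 1 added. For illustration, assume independent draws with abnormality probability p per draw. The chance of at least one abnormal value is 1 − (1 − p)^n.

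| p (assumed) | n = 13 | n = 14 | n = 16 |
|---|---|---|---|
| 1% | 12.2% | 13.1% | 14.9% |
| 5% | 48.7% | 51.2% | 56.0% |

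The follow-up draw alone adds about 0.9 points at p = 1% and 2.6 points at p = 5%. Repeated values within a subject are correlated, so these figures are only a guide.

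**The case against.** The best defence is that the words mean only that the extreme is not tied to a visit window, so unscheduled draws count. The row label, the opening rule of 7.11.6 and the EOT wording of Table 23 all point to on-treatment data. The Week 12 rows may be bounded simply because placebo subjects change drug then. This much stands: a reader might infer that the plan has decided to count screening and follow-up values, but the documents contain an unresolved conflict, not a settled rule.

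Other stronger inferences also fail:

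- That follow-up draws sit mainly in the etanercept arm. Withdrawn subjects in every arm, and ASP015K completers who do not start the extension at once, are also due follow-up, and uptake is not given.
- That pre-dose values reach the worst categories. Criterion 13 keeps them out of the most severe Table 7 bands for the parameters it caps; CPK is the exception.
- That arm differences shrink by a definite factor. This needs the share of subjects abnormal only before dosing, which the documents do not give.
- That the placebo comparison is compromised. It uses the bounded Week 12 rows. The overall shift tables have no placebo column, and 7.5.2 plans no hypothesis tests on laboratory data.

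Wide capture could also be deliberate, since SAP 7.5.1 treats adverse events through follow-up as treatment emergent. But SAP 6.2 stops at Week 52 or withdrawal, and neither supports pre-dose values in an on-treatment row.

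One objection shapes the remedy. CPK retests after suspension (Protocol 5.4.4.1) and liver retests 48 to 72 hours after notification (Protocol Appendix 4) may fall later than last dose +2 days. A hard cut with later values only listed could lose confirmatory results from the summaries.

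**Conclusion.** The point holds as a contradiction in the SAP that needs settling before programming. Followed literally, the overall rows put pre-dose and off-drug values into on-treatment Table 7 counts, and allow a screening or follow-up value to create a false shift from baseline. A completer could contribute up to three extra scheduled chemistry and haematology draws.

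The arms would have unequal opportunity for an extreme at follow-up. The etanercept share of those draws runs from 50% to 95% as f falls from 100% to 5%, and the documents do not say where in that range the trial lies. The number of subjects who would be misclassified cannot be estimated from the documents. Neither the primary endpoint nor the Week 12 laboratory comparison with placebo is touched.

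**What to change.** In Tables 12 and 13, replace the unlimited period with values after the first dose (Day 2 onward), scheduled and unscheduled, up to the section's own cut-off: last dose +2 days for study drug, +9 days for the reference drug. State the same window in 7.5.2.1 and Table 23.

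Add a companion summary, not only a listing, that extends the window to include post-treatment values, so that confirmatory CPK and liver retests after stopping drug remain visible. Label it as including off-drug data, and note that follow-up draws are not equally available across arms.

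The cost is SAP wording, one date filter and one extra table.

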7.11.7 Handling of Schedule of Assessments of Pharmacodynamic Variables

For data obtained after the end of study treatment, the data obtained within + 2 days after the last dose is taken will be included in analysis. For data after the end of reference treatment, data obtained within + 9 days after the last dose will be included in analysis. Baseline for safety is defined as last non-missing value before the first dose of study drug or reference drug for all subjects including placebo assigned subjects. For Week 12/ET, the values at closest date to reference date will be used. As for the subjects who switched to receive ASP015K instead of placebo, the last observation before first dose of ASP015K at Week 12 will be used for the analysis for visit Week 4, 8, 12, 12/ET. For EOT, the closest value to the reference date will be used regardless of the switching from placebo.

(1) Biomarkers and lymphocyte subsets

Table 17. Visit Window for Pharmacodynamic Variables

Time points defined in analysis	Reference date*	Acceptable time range
Baseline	Day 1	Before the initiation of treatment with the study drug or reference drug on Day 1
Week 4 to Week 28**	Day $7 \times x + 1$	Day $(7 \times x - 6)$ to Day $(7 \times x + 8)$ and before the initiation of treatment with the study drug or reference drug on the visit day
Week 52	Day 365	Day 358 to Day 372
Week 12/ET (Week 12 or at early termination before Week 12)	Day 85	Day 2 to Day 92
EOT (Week 52 or at early termination)	Day 365	Day 2 to Day 372

*: Day 1 represents the first day of study or reference treatment.

** : Represents the reference date and acceptable time range for Week x.

8 DOCUMENT REVISION HISTORY

Version	Date	Changes	Comment/rationale for change
1.00	26-Dec-2016	NA	Document finalized for TFDA submission
2.00	19-Jan-2018	Modifications as appropriate	Document finalized
2.10	19-Jan-2018	Add multiple imputation to sensitivity analysis	Document finalized

10 APPENDICES

10.1 Appendix 1: Overview of ACR20 response at Week 12/ET

Table 18 summarizes the analyses of the ACR20 response at Week 12/ET, with "X" indicating that the variable will be analyzed. All analyses will be based on the FAS for Initial randomization group, unless otherwise specified.

Table 18. Overview of ACR20 response at Week 12/ET

Analysis Type	Analysis Variable	Analysis Method
Primary / Sensitivity / Subgroup/ Adjustment for imbalance/ Japanese subjects	Primary: ACR20 response at Week 12/ET	
Primary	X ¹	Logistic regression
Sensitivity² (see Sections 7.4.1.2 and 7.11.2 for further explanation)		
LOCF and NRI	X	Logistic regression
PPS as analysis set	X	Logistic regression
Observed data	X	Logistic regression
Multiple Imputation Assuming Missing at Random	X	Logistic regression
Placebo Multiple Imputation (pMI)	X	Logistic regression
Interaction³ (see Sections 7.4.1.3 for further explanation)		
the prior biologic-DMARD-IR x treatment group interaction	X	Logistic regression ⁴
concomitant DMARD use x treatment group interaction	X	Logistic regression
study region x treatment group interaction	X	Logistic regression
Subgroup⁵		
Sex	X	Logistic regression ⁶
Age Group	X	
Prior Anti-TNF DMARD Use	X	
Prior Biologic DMARD-IR	X	
Concomitant DMARD Use at Baseline	X	
Study Region	X	
Baseline DAS28-CRP (<= 3.2, 3.2 <- 5.1, > 5.1)	X	
Baseline DAS28-ESR (<= 3.2, 3.2 <- 5.1, > 5.1)	X	

Duration of RA	X	
Number of Prior DMARDs Used	X	
Number of Prior Biologic DMARDs Used	X	
MTX Dose at Baseline	X	
Baseline CRP (< 1.0, >= 1.0)	X	
Concomitant DMARD Category at Baseline	X	
Protocol Version Number	X	
Concomitant Steroid at Baseline	X	
Prednisone Dose at Baseline	X	
Adjustment for imbalance⁷		
Adjusted analysis	X	Only in the case of imbalance presented. Logistic regression ⁸
Japanese subjects⁹		
Analysis for Japanese subjects	X	Logistic regression

Abbreviations are defined in Section I.
 
¹ Based on FAS as analysis set, logistic regression model with treatment group as the factor and the prior biologic-DMARD-IR, concomitant DMARD use, and study region as the covariates, 7.11.2 Table 8. 1. LOCF components will be used.
 
² For the sensitivity analysis, multiplicity adjustment is not executed.
 
³ For the interaction analysis, multiplicity adjustment is not executed.
 
⁴ Logistic regression model including each interaction term separately will be performed.
 
⁵ Subgroup categories are provided in Section 7.8. For the sensitivity analysis, any statistical testing is not executed.
 
⁶ Logistic regression model will be performed for each subgroup category.
 
⁷ The variables in which imbalance is evaluated are provided in Section 7.2.2. For the adjusted analysis, multiplicity adjustment is not executed.
 
⁸ Logistic regression model with adjusted variable (if imbalance will be detected) added to primary analysis logistic regression model (Section 7.4.1.1).
 
⁹ For analysis for Japanese subjects, multiplicity adjustment is not executed.
		

